## STUDY DESIGN

### Treatment Regimen and Duration of Therapy

All patients will sign an informed consent which explains the rationale for closing the CO-1686 clinical development program for NSCLC and the option for ongoing patients to continue

receiving study treatment, should they decide to do so and/or if in the opinion of their treating physician they continue to receive clinical benefit. No patient will commence treatment under this amendment until appropriate IEC/IRB approval of the study protocol has been received.

Patients may continue to receive CO-1686 if the PI and patient deem it is appropriate for the patient though the availability and suitability of alternative treatment options should be considered by the treating physician and discussed with the patient. CO-1686 will be administered daily on a 21-day cycle. Dosing will be delayed or decreased according to protocol-specified toxicity criteria ([Section 7.4.3](#)). Each dose should continue to be taken with 8 oz. (240 mL) of water and with a meal or within 30 minutes after a meal two times per day. Tablets should be swallowed whole.

Treatment may continue until disease progression or intolerable toxicity. Please note, patients may opt to continue to receive treatment with CO-1686 following radiographic progression as outlined in the NCCN guidelines for treatment of NSCLC with EGFR TKIs if patient provides additional consent, the investigator feels it is in the patient's best interest and with sponsor approval. In general, eligible patients may include those with asymptomatic systemic progression or locally symptomatic progression, such as brain metastases amenable to local treatment, with concomitant asymptomatic systemic progression or continued systemic disease control. This must be discussed with the sponsor and will be reviewed on a case-by-case basis.

If a patient continues treatment post-progression, all Extension Phase study assessments should continue per protocol and data should be captured in the eCRF. The patient should be discontinued from treatment once it is clear that no further clinical benefit can be achieved.

Both the hyperglycemia and QTc management guidelines ([Section 7.4.3](#)) should be followed during this extension phase and any modifications/ deviations from these guidances should be discussed and agreed upon with the sponsor prior to implementation.

Formal safety data reviews will continue approximately every 6 months once enrollment is completed and as long as patients remain on treatment. The review committee includes external experts and sponsor personnel. The external experts will include, but not be limited to, the coordinating PIs of the study. The sponsor's reviewers will include the Medical Monitor and additional Clovis medical experts, and a biostatistician. The protocol will be amended as appropriate to incorporate additional patient safety monitoring if new safety signals or a change in risk:benefit are noted at any review.

Once study treatment has been discontinued and the End of Treatment visit has been completed, study participation will cease. Investigational centers will interpret tumor scans locally for the purpose of making treatment decisions and for final tumor response evaluation. The study will close once all patients have either completed participation, have transferred to a locally approved treatment access program (e.g. a named patient program) in accordance with relevant local regulations or the sponsor decides to close the study.

## **PATIENT ELIGIBILITY AND WITHDRAWAL CRITERIA**

### **Eligibility and Number of Patients**

This amendment applies to patients who remain on CO-1686 treatment in the CO-1686-008 study. No additional patients will be enrolled.

### **Withdrawal Criteria**

The patient has the right to stop treatment or to withdraw from the study at any time.

Patients will continue to receive treatment until one of the following cessation criteria applies:

- Disease progression (PD) based on tumor scans or clinical status assessed by the investigator.
  - Post-progression treatment is permitted, at the discretion of the Investigator and with the approval of the sponsor.
- Intercurrent illness that prevents administration of treatment (Reference Section 7.7)
- Unacceptable toxicity.
- Patient withdrawal of consent to further treatment.
- Major noncompliance that may affect patient safety.
- Pregnancy.
- Investigator decision.

In addition, the sponsor may discontinue the trial early for any of the reasons noted in [Section 13.6](#) of the protocol.

The date and reason for cessation of treatment will be documented. Patients with ongoing SAEs will be followed until either resolution or stabilization has been determined.

## **STUDY PROCEDURES**

### **Schedule of Assessments**

The procedures and assessments to be performed are outlined in the Schedule of Assessments presented in Appendix D, Table 4. Procedures are synchronized with administration day of treatment unless indicated. The revised evaluations should commence immediately after the patient is consented, maintaining previous treatment cycle and day sequence.

**Appendix D, Table 4: Protocol CO-1686-008 Schedule of Assessments – Extension Phase (Phase 1 and Phase 2 Patients)**

	Prior to beginning Amendment 8 Evaluations	Day 1 of each cycle	End of Treatment (28±7 days after last dose)
Informed consent	X		
Physical Examination including vision check		X	X
Vital Signs a and Weight		X	X

Concomitant Medications and Procedures		X	X
Contraceptive Counseling b			X
Serum Pregnancy Test c			X
Local fasting Serum Chemistry d		X	X
Local Hematology d		X	X
Adverse Events (AE) Monitoring e		X	X
Patient Diary f		X	X
CO-1686 Dispensing / Administration		X	
ECG Assessments using central ECG machine g		X	X
Tumor Scans h	To be performed per institutional standard of care or every 3 cycles; scans are not required at the End of Treatment Visit		
Blood for CYP Evaluation (Optional Sampling) i		X	

a = Vital signs (blood pressure, pulse, and temperature) taken predose on drug administration days.

b = Patients are to continue using effective contraception for 12 weeks after last dose of CO-1686 and report any pregnancies during this period.

c = Serum β-hCG to be evaluated by local lab and performed only on women of childbearing potential.

d = Glucose must be measured following an 8 hour fast (no food or liquid other than water). Hemoglobin A1c will be measured on Day 1 of every other cycle while the patient is on study. Samples should be analyzed by local laboratory.

e = Patients will be monitored for AEs from the time the first dose of CO-1686 is administered through 28 days after the last dose.

f = Patient diaries should be collected and reviewed for compliance at each visit. No diary will be dispensed at end of treatment.

g=12-lead ECG (in triplicate, 10-sec tracings > 2 min apart) prior to dosing up to and including Cycle 12, at a minimum. For patients who are ongoing at this time and for whom QT has been < 470 ms throughout the study, ECG monitoring may be subsequently taken every 3rd cycle thereafter. ECGs will be performed and interpreted locally for patient care decisions; however, tracings should be submitted to the central lab for independent evaluation.

h=Tumor scans will no longer be required to be submitted to a central reviewer; Disease progression to continue to be assessed locally by the Investigator. If a patient discontinues treatment before progression or is continuing treatment post progression (approval from Sponsor is required), then the decision to conduct additional scans and the frequency of those scans to monitor disease progression will be the responsibility of the treating physician.

i=Only one sample is needed and may be collected at any visit to enable NAT2 analysis.

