### **ECG Monitoring and Effect on QTc**

Serial ECG monitoring is performed on all patients in Phase 1, at baseline, on Cycle 1 Day 1 and Cycle 1 Day 15 (prior to dosing and at the multiple time points as described in [Table 13](#) following dosing with CO-1686), and on Day 1 of all subsequent cycles (prior to dosing and at the estimated  $T_{max}$  (2 hours) postdose), at the End of Treatment, and as clinically indicated on all patients in order to assess the effect of oral CO-1686 on the QTc interval. All Phase 1 ECGs will be performed on equipment provided by the sponsor (or designee) and reviewed by site personnel and a core/central laboratory.

Triplet ECG monitoring will be conducted as indicated up to and including Cycle 12 for all patients. For patients who are ongoing at this time and for whom QT has been  $< 470$  ms throughout the study, ECG monitoring may be subsequently reduced to predose evaluation and taken every 3rd cycle thereafter.

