### 6.3 Exclusion Criteria

Any of the following criteria will exclude patients from study participation:

1. Documented evidence of an Exon 20 insertion activating mutation in the EGFR gene
2. Active second malignancy, i.e. patient known to have potentially fatal cancer present for which he/she may be (but not necessarily) currently receiving treatment.
  - Patients with a history of malignancy that has been completely treated, with no evidence of that cancer currently, are permitted to enroll in the trial provided all chemotherapy was completed > 6 months prior and/or bone marrow transplant > 2 years prior
3. Known pre-existing interstitial lung disease
4. Patients with Leptomeningeal carcinomatosis are excluded. Other CNS metastases are only permitted if treated, asymptomatic, and stable (not requiring steroids for at least 4 weeks prior to start of study treatment).
5. Treatment with prohibited medications [e.g., concurrent anticancer therapy including other chemotherapy, radiation treatment or hormonal treatment (except corticosteroids and megestrol acetate), or immunotherapy] ≤ 14 days prior to treatment with CO-1686
6. Patients who are currently receiving treatment with any medications that have the potential to prolong the QT interval and the treatment cannot be either discontinued or switched to a different medication before starting CO-1686
  - see <http://crediblemeds.org/> for a list of QT-prolonging medications
7. Prior treatment with CO-1686 or other drugs that target T790M positive, mutant EGFR with sparing of wild type EGFR, e.g., AZD9291, HM61713, TAS-121
8. Any of the following cardiac abnormalities or history:
  - a. Clinically significant abnormal 12-lead ECG, QT interval corrected using Fridericia's method (QTcF) > 450 msec
  - b. Inability to measure QT interval on ECG
  - c. Personal or family history of long QT syndrome
  - d. Implantable pacemaker or implantable cardioverter defibrillator
  - e. Resting bradycardia < 55 beats/min
9. Non-study related surgical procedures ≤ 7 days prior to administration of CO-1686. In all cases, the patient must be sufficiently recovered and stable before treatment administration
10. Females who are pregnant or breastfeeding
11. Refusal to use adequate contraception for fertile patients (females and males) for 12 weeks after the last dose of CO-1686

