### Management of Prolonged QTc

ECGs will be measured throughout the study as described in the protocol. Readings for QT prolongation will be based on the average seen in the ECGs for each time point. Patients are required to have within-normal-range potassium and magnesium at enrollment, and these electrolytes should be maintained within range during CO-1686 treatment, if necessary using supplementation. If QTc prolongation of CTCAE Grade 3 are observed, CO-1686 will be held until the event has improved to Grade 1. CO-1686 can then be re-started at a reduced dose upon approval by the sponsor. After two dose reduction evaluations, if CTCAE Grade 3 or above QTc prolongation recurs, then CO-1686 will be discontinued unless agreed with the sponsor that additional dose reduction can be evaluated. If QTc prolongation changes of CTCAE Grade 4 are observed at any time, CO-1686 will be discontinued permanently.

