#### Additional information relating to Hyperglycemia and QTc prolongation

The polymorphic enzyme NAT2 mediates the N-acetylation of M502 to form M544 and also plays a role in the elimination of M460. NAT2 genotype polymorphism was assessed for the group of patients who received rociletinib at 500 mg BID, 625 mg BID, 750 mg BID, and 1000 mg BID and who gave additional informed consent for genomic testing. The NAT2 genotype polymorphism testing was performed using an assay based on polymerase chain reaction (PCR) followed by mass spectrometry to identify single nucleotide polymorphisms in NAT2. Based on NAT2 genotype results, patients were classified as having "low", "intermediate", and "rapid" acetylator phenotype. Acetylator status is currently available for 635 patients. Additional testing will be completed as additional samples are received.

Adverse event and laboratory data based on NAT2 phenotype are summarized in Appendix D, [Appendix D, Table](#), [Appendix D, Table](#), and [Appendix D, Table](#). Analyses are presented by acetylator status for all doses combined, since the combined-dose findings were consistent with the findings within each dose group.

[Appendix D, Table](#) demonstrates that Grade 3 events are less common in patients who are classified as "rapid" acetylators. As expected, the relationship is most clear for hyperglycemia and QT-prolongation, while other adverse events of special interest (AESIs) appear to be less closely associated with acetylator status. [Appendix D, Table](#) shows that hyperglycemia appears to be less frequent and less severe in rapid acetylators. [Appendix D, Table](#) shows that QTcF prolongation on ECG appears to be less frequent and less severe in rapid acetylators.

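### The Extension Phase rule for spacing out ECGs is set on QT, without naming QTcF, although eligibility uses QTcF and the hold and stop rules use QTc

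*Protocol*

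**What the plan says.** Appendix D replaces the Section 9.1 schedules for every patient still on treatment. Table 4, footnote g, requires triplicate ECGs on Day 1 of each cycle through at least Cycle 12. After that, ECGs may be taken every third cycle in ongoing patients "for whom QT has been < 470 ms throughout the study". The Day 1 procedures in Appendix D repeat the criterion in the same terms. Footnote g has sites read the ECGs locally for care decisions, and adds that "tracings should be submitted to the central lab for independent evaluation".

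The other QT thresholds that govern patients are corrected for heart rate:

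- Section 6.3, exclusion 8a, uses "QT interval corrected using Fridericia's method (QTcF) > 450 msec".
- Section 7.4.3 holds CO-1686 for Grade 3 QTc prolongation and stops it permanently for Grade 4. Appendix D keeps these rules: "Both the hyperglycemia and QTc management guidelines" of Section 7.4.3 continue to apply.
- The Extension Phase's own risk summary (Appendix D, Table 3) is in QTcF.

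Protocol Section 11.2.10.5 and SAP Section 14.4 both classify QT and QTc as two separate variables.

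**The concern.** The one patient-management threshold without a correction is the one that relaxes monitoring. Section 3.4.1 states that CO-1686 lengthens QTc. Because footnote g leaves care decisions to local reading, each site applies the criterion itself, and nothing in either document tells it to use a corrected value. The hold and stop rules act only on ECGs that are taken, and this criterion decides how often they are taken. A patient restarted at a reduced dose after Grade 3 prolongation, which Section 7.4.3 allows with sponsor approval, could qualify for sparser ECGs if uncorrected QT had stayed under 470 ms. The Extension Phase schedule also lists only the predose ECG on Day 1 and no longer the 2-hour one, so fewer ECGs remain to show a problem.

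**Working it through.** The plan gives no figure to reproduce for this criterion. The check compares the criterion as worded with the same cut-off applied to QTcF.

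**Inputs.** Cut-off 470 ms (Appendix D, Table 4, footnote g). Cycle length 21 days. Fridericia correction, as in exclusion 8a. Heart rates are assumed, because the documents give none for patients on treatment.

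**Formula.** QTcF = QT × (HR/60)^(1/3).

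**1. Above 60 bpm the literal rule is too lenient.** Take QT = 469 ms, which passes:

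| Heart rate (bpm) | QTcF (ms) |
|---|---|
| 60 | 469.0 |
| 65 | 481.7 |
| 70 | 493.7 |
| 72 | 498.4 |
| 73 | 500.7 |

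For comparison, SAP Section 14.4 describes the Grade 3 criterion as at least two on-treatment QTc values above 500 ms.

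**2. Below 60 bpm it is too strict.** The QT that corresponds to QTcF 470 ms is 470 / (HR/60)^(1/3): 475.3 ms at 58 bpm and 483.8 ms at 55 bpm. This side is bounded at entry, since exclusion 8e removes "Resting bradycardia < 55 beats/min".

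**3. When can a patient with QTcF 500 ms pass?** QTcF of 500 ms means QT of at least 470 ms at any rate up to 60 × (500/470)^3 = 72.2 bpm. Such a patient passes only if the rate is above about 72 bpm at every ECG showing that value.

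**4. How many ECGs must pass?** The condition covers the whole study. From Table 13, an ordinary Phase 2 patient has 1 at screening, 4 in Cycle 1 (Days 1 and 15, predose and 2 h) and 11 × 2 = 22 in Cycles 2 to 12, so up to 27 time points. There are fewer if the patient moved to the Extension Phase before Cycle 12. Phase 1 patients and the full-PK subset have seven ECG time points on each of two Cycle 1 days, so 1 + 14 + 22 = 37.

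**5. What changes?** The ECG interval goes from 3 weeks to 3 × 3 = 9 weeks, after 12 × 3 = 36 weeks of treatment.

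**6. How common are high QTcF values?** Appendix D, Table 3, counts QTcF of at least 501 ms in 59 + 22 + 1 = 82 of 635 genotyped patients (12.9%), and at least 481 ms in 92 + 44 + 7 = 143 of 635 (22.5%). The table prints 31% beside the 59 of 300 slow acetylators, but 59/300 is 19.7%; I use the counts. These are any post-baseline values at all doses combined. They show that the range in step 1 occurs in these patients. They do not estimate how many would be misclassified.

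**The case against.** The strongest reply is that QT here is plain shorthand. In Sections 5.1.2 and 5.1.3 the same criterion sits under a heading on QTc, and Section 5.1.2 says those ECGs are taken "in order to assess the effect of oral CO-1686 on the QTc interval". Section 7.4.3, inside its QTc rules, writes "Readings for QT prolongation will be based on the average seen in the ECGs for each time point". Appendix D says "the relationship is most clear for hyperglycemia and QT-prolongation" where its Table 1 has QTc prolongation. Fridericia is the protocol's lead correction throughout, and the places that separate QT from QTc are statistical summaries, not clinical rules. Section 9.8.1.4 also refers sites to an investigator's file that is not available here. I accept that shorthand is the likelier reading. It remains an inference, and if it is right, the edit only records what was meant.

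The second reply is that the path to harm is narrow. The reduction is optional and comes only after 12 cycles, and every ECG must have passed. Reported QTc onset is between Days 1 and 15, so most prolongation should show while ECGs are still taken every cycle. QT-prolonging co-medication calls for extra ECGs (Section 8), tracings still go to the central laboratory, and safety reviews continue about every 6 months. All of this stands and limits the size of the point. But neither the central reading nor the reviews are stated to check who qualifies for fewer ECGs.

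Third, the wording is inherited from the main protocol and enrollment is closed. A patient enrolled by 31 December 2014 and still treated in June 2016 would be about 74 weeks in, or 74/3 ≈ 25 cycles, so the Cycle 12 decision would normally have come before Amendment 8. That is fair, but the condition covers the whole study and still governs these patients under Appendix D.

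Finally, the hold and stop rules say QTc without naming Fridericia, so choosing QTcF is itself an inference. It rests on exclusion 8a and on the protocol's use of QTcF in its ECG result tables.

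**Conclusion.** The point holds. The criterion that relaxes ECG monitoring is written on a different variable from the eligibility, hold and stop rules, and no text equates them. Read literally, it can pass a patient with QTcF of about 482 to 501 ms at 65 to 73 bpm, and can hold back one with QTcF under 470 ms at rates below 60 bpm. These are calculated single values at assumed heart rates. The number of patients affected cannot be computed, because neither document gives a QT or heart-rate distribution. Practical exposure is limited by the safeguards above. No endpoint, sample size or analysis is affected. This is a clarification of a safety threshold that should be made. My confidence is medium, because the intended meaning was probably QTc all along.

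**What to change.** Replace QT with QTcF in the 470 ms criterion in Appendix D, Table 4, footnote g, and in the Appendix D Day 1 procedures. These are the two operative places for ongoing patients, and a clarification letter or the next amendment would do. For consistency only, make the same edit where the criterion recurs: the ECG paragraphs of Sections 5.1.2 and 5.1.3, Table 13 Note 2, and Sections 9.4.1, 9.5.5 and 9.8.1.4.

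The cost is one word in each place. Some patients with faster heart rates would stay on ECGs every 3 weeks instead of every 9. A few with rates below 60 bpm could qualify for fewer ECGs than the literal wording allows. Because the condition covers the whole study, sites should also recheck anyone already on the reduced schedule against QTcF.

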## **Day 1 of Each Cycle**

Patients will be instructed to **refrain** from taking their dose of oral CO-1686 at home on the day of their clinic visit (Day 1 of the cycle) because the dose will be taken during the clinic visit. The following procedures will be completed:

### **The following procedures are conducted before dosing with CO-1686:**

- Physical examination
  - Including a vision check as part of a standard physical exam
- Weight
- Vital signs (blood pressure, pulse, and temperature)

- 12-lead ECG (in triplicate, 10-sec tracings > 2 min apart) using central ECG machine prior to dosing up to and including Cycle 12. For patients who are ongoing at this time and for whom QT has been < 470 ms throughout the study, ECG monitoring may be subsequently taken every 3rd cycle thereafter. ECGs will be performed and interpreted locally for patient care decisions; however, tracings should be submitted to the central lab for independent evaluation.
- Fasting serum chemistry (includes fasting glucose) HbA1c will be measured every other cycle (Day 1 of Cycle 3, 5, 7 etc).
- Hematology
- Concomitant medications and procedures
- AE monitoring
- Collection and review of patient diary
- Dispense capsules or tablets to patient
  - Oral CO-1686 will be administered with a meal, or within 30 minutes after a meal. The patient must also drink at least 8 ounces (240 mL) of water when taking CO-1686. Tablets should be swallowed whole.
- Dispense patient diary to patient
- (Optional) Blood for CYP Evaluation
  - Patient may consent for optional CYP sample collection if not previously collected already, and have the sample collected for NAT2 analysis
  - Sample should only be collected at a single visit

**The following procedure is conducted irrespective of dosing time:**

- Tumor scans per institutional standard of care or every 3 cycles (between Days 14 and 21). until disease (tumor or clinical) progression. Disease progression to continue to be assessed locally by the Investigator. If a patient discontinues treatment before progression or is continuing treatment post progression (with approval from Sponsor), then the decision to conduct additional scans and the frequency of those scans to monitor disease progression will be the responsibility of the treating physician.

